5.2.3. Efficacy analysis

Linear advance of the wound margin

Computation of **linear advance** of the wound margin towards the wound center from baseline:

$$\bar{d} = \frac{\Delta A}{\bar{p}}$$

Where ΔA is the difference in the area ($A_{\text{visit}} - A_{\text{baseline}}$) and p the average of the wound perimeter:

$$(\bar{p} = \frac{P_{\text{visit}} + P_{\text{Baseline}}}{2})$$

Computation of **linear advance** of the wound margin towards the wound center from previous visit:

$$\bar{d} = \frac{\Delta A}{\bar{p}}$$

Where ΔA is the difference in the area ($A_{\text{visit } v} - A_{\text{visit } v-1}$) and p the average of the wound perimeter:

$$(\bar{p} = \frac{P_{\text{visit } v} + P_{\text{visit } v-1}}{2})$$

Pain intensity

Pain intensity is defined as the Visual Analog Scale (VAS) values.

In case of response “No” to the question “Does the participant feel any pain or discomfort related to his/her leg ulcer?” and the VAS value is missing this value will be imputed to zero.

Diabetic status

For efficacy analysis, a patient with $\text{HbA1c} \geq 6.5\%$ or a medical history in the following list : 1689.2 Evidences of diabetes mellitus M220 is considered as diabetic.

5.2.4. Safety analysis

5.2.4.1. Adverse events

Each **medical concept of adverse event coded according to the internal "multiple medical concept" process** is taken into account as a single adverse event in the statistical analysis. The modalities of the adverse event (onset and end dates, intensity, seriousness, action taken, additional therapy, relationship, outcome...) replicated by default to each medical concept are also taken into account in the statistical analyses.

5.3. Statistical methods details

5.3.1. MCPMod method for primary analysis

The MCPMod method is presented in details in the following paragraph.

Let Y_{ij} be the relative change from baseline at W004 for the patient j treated at the dose i of S42909.

We assume that:

$$Y_{ij} = \mu_i + \varepsilon_{ij}$$

$$\varepsilon_{ij} \stackrel{ind}{\sim} N(0, \sigma^2)$$

Where:

- $\mu_i = f(d_i, \theta)$ is the mean response at dose d_i for the dose response models $f(\cdot)$ parameterized by a vector of parameters θ .
- $i = 1, \dots, k$ where k is the number of dose.
- $j = 1, \dots, n_i$ where n_i the number of patients at the dose i .
- ε_{ij} is the error term for patient j within dose group i . ε_{ij} follows a normal distribution with mean 0 and variance σ^2 .

Dose-finding will be performed using a set of candidate models of $f(\cdot)$. The candidate models are set up using the hypothesized dose-response functions as follows:

$$f(d, \theta) = a + b g(d, \theta_0)$$

where $g(\cdot)$ is the standardized form of the dose-response function with θ_0 denoting the vector of initial values of the model parameters or guesstimates that are derived from the expected shape of the dose-response relationship. Further, a is the location parameter, and b is the scale parameter.

Dose response models are defined in the [Table \(5.3.1\) 1](#).

Table (5.3.1) 1 - Dose-response models

Model	$f(d, \theta)$	$g(d, \theta_0)$
Linear	$E_0 + \delta d$	d
Emax	$E_0 + \frac{E_{max}d}{ED_{50} + d}$	$\frac{d}{ED_{50} + d}$
Sigmoid Emax	$E_0 + \frac{E_{max}d^h}{ED_{50}^h + d^h}$	$\frac{d^h}{ED_{50}^h + d^h}$
Exponential	$E_0 + E_1(\exp\left(\frac{d}{\delta}\right) - 1)$	$\exp\left(\frac{d}{\delta}\right) - 1$
Logistic	$E_0 + \frac{E_{max}}{(1 + \exp\left(\frac{ED_{50} - d}{\delta}\right))}$	$\frac{1}{(1 + \exp\left(\frac{ED_{50} - d}{\delta}\right))}$

In this study, dose-finding will be performed using the following set of m candidate models of $f(\cdot)$ defined by some couples (d^*, p^*) (dose, percentage of efficacy at this dose):

- Linear.
- Emax1 (200 mg, 90%).
- Emax2 (400 mg, 70%).
- Sigmoid Emax (200 mg, 10%) and (1000 mg, 90%).
- Logistic (200 mg, 10%) and (1000 mg, 90%).
- Exponential1 (400 mg, 10%).
- Exponential2 (800 mg, 10%).

The parameter values for each candidate model corresponding at the set of candidate models are mentionned in the Table (5.3.1) 2.

Table (5.3.1) 2 - Dose-response models parameters

Candidate model	Parameter values (θ)
Linear	$E_0 = 32.5, \delta = 0.025$
Emax 1	$E_0 = 32.5, E_{max} = 30.6, ED_{50} = 22.2$
Emax 2	$E_0 = 32.5, E_{max} = 34.3, ED_{50} = 171.4$
Sigmoid Emax	$E_0 = 32.5, E_{max} = 32, ED_{50} = 447.2, h = 2.7$
Logistic	$E_0 = 31.3, E_{max} = 32.3, ED_{50} = 600, h = 182.1$
Exponential 1	$E_0 = 32.5, E_1 = 1.95, \delta = 428.9$
Exponential 2	$E_0 = 32.5, E_1 = 0.03, \delta = 174.4$

Optimal contrasts

The MCPMod procedure is based on a multi-contrast test. A unique dose-response contrast is associated with each dose-response model. This contrast is defined as the contrast that has the highest power, *i.e.*, the highest probability of rejecting the associated null hypothesis of no effect, under this particular model. The standardized version of the model is used and the predicted effects is computed under this standardized model:

$$u_{ij} = g_i(d_j, \theta_0)$$

Where:

- $j = 0, \dots, m$, with m the number of candidate model.
- i the dose.

The predicted effects can be computed using the initial values defined in the [Table \(5.3.1\) 1](#).

The optimal constraint is calculated from the predicted effects by centering and normalizing this vector.

The coefficients of the optimal constraint for each model are defined with the following formula:

$$c_{ij} = \frac{u_{ij} - \frac{1}{m+1} \sum_{l=0}^m u_{il}}{\sqrt{\sum_{l=0}^m (u_{ij} - \frac{1}{m+1} \sum_{l=0}^m u_{il})^2}}, j = 0, \dots, m$$

Where

- $j = 0, \dots, m$, with m the number of candidate model
- i the dose

Dose-response tests

The significance of the dose-response trend based on each model-specific contrast will be assessed using the following t statistics:

$$t_m = \frac{\sum_{i=1}^k c_{mi} \bar{Y}_i}{S \sqrt{\sum_{i=1}^k \frac{c_{mi}^2}{n_i}}}$$

where

- \bar{Y}_i is the empiric mean of the response within dose group d_i .
- m is the number of model.
- n_i is the number of patients within the dose group d_i .
- $S^2 = \sum_{i=1}^k \sum_{j=1}^{n_i} \frac{(Y_{ij} - \bar{Y}_i)^2}{N - k}$
- c_m is the vector of contrasts with $\sum_{i=1}^k c_{mi} = 0$

The dose-response tests identify the set of clinically relevant models. A multiplicity adjustment is taken into account in MCP. The joint distribution of the m test statistics is taken into account to compute an adjusted critical value that defines the threshold for statistical significance.

Under the global null hypothesis of no treatment effect under any model, the test statistics follow a central multivariate t distribution with $N - k$ degrees of freedom and correlation matrix R .

The correlation between the test statistics t_i and t_j is given by:

$$\rho_{ij} = \frac{\sum_{l=0}^m c_{il}c_{jl}}{\sqrt{\sum_{l=0}^m c_{il}^2 \sum_{l=0}^m c_{jl}^2}}$$

To derive the multiplicity-adjusted critical value, denoted by q , let $T_1; \dots; T_m$ denote the random variables that have the same joint distribution as $t_1; \dots; t_m$ under the global null hypothesis. The adjusted critical value q is found from:

$$\Pr(T_{max} > q) = \alpha$$

where α is the pre-specified Family Wise Error Rate (FWER) level equal to 0.025 (one-sided test).

The set of clinically relevant dose-response model corresponds to the models associated with $t_i > q$. Adjusted p-value will be calculated according to the value of q .

Among the set of clinically relevant dose-response models, the best dose-response contrast will be identified as the contrast test with the maximum test statistic.

An estimation of parameters of the best model selected will be provided as well as a plot of this model.

5.3.2. MCPMod method with covariate-adjusted inferences

The MCPMod method was originally introduced for developing robust dose-response evaluation strategies in Phase II trials with simple primary analyses, e.g., analyses without covariate adjustment ([Bretz, Pinheiro and Branson, 2005](#)). The original method was later extended in multiple directions. [Pinheiro et al. \(2013\)](#) demonstrated how a generalized version of the MCPMod approach can be set up to enable covariate-adjusted inferences in the primary analysis.

The general MCPMod method proposed in [Pinheiro et al. \(2013\)](#) will be applied to the primary endpoint in the FAS. This endpoint is assumed to be normally distributed and will be analyzed using an analysis of covariance (ANCOVA) model adjusted for two stratification factors (combined prognosis criteria and diabetic status).

The general MCPMod method will be applied to the seven pre-defined dose-response models (see definition in [Table \(5.3.2\) 1](#)) with the 6 doses. The models will be denoted by $f_i(d, \beta)$, $i = 1 \dots, 7$, where d is the dose and β is a vector of model parameters, and the doses will be denoted by d_1, \dots, d_6 .

The method will be implemented as follows. As the very first step, initial values of the model parameters will be selected for the pre-defined models. The column vector of initial values for the i th model will be denoted by b_i , $i = 1 \dots, 7$. Let μ_i denote the column vector of mean effects computed from the i th model using these initial values of the model parameters, i.e., $\mu_{ij} = f_i(d_j, b_i)$, $i = 1 \dots, 7$, $j = 1 \dots, 6$.

The ANCOVA model without an intercept adjusted for the two stratification factors will be fitted to the data. Let $\hat{\mu}_j$ denote the covariate-adjusted mean effect in the j th dose group, $j = 1 \dots, 6$, and let $\hat{\mu}$ denote the column vector of covariate-adjusted mean effects. Also, let S denote the covariance matrix for these mean effects estimated from the ANCOVA model.

The optimal dose-response contrasts will be found by computing the following set of vectors:

$$c_i = S^{-1} \left(\mu_i - \frac{\mu'_i S^{-1} I}{I' S^{-1} I} \right),$$

where the prime denotes transposition and I is a column vector of 6 ones, i.e., $I' = (1 \ 1 \ 1 \ 1 \ 1 \ 1)$. After that each vector is normalized, i.e., $c_i = c_i / |c_i|$. The resulting column vector c_i is the optimal dose-response contrast for the i th model, $i = 1 \dots, 7$.

Let C denote the contrast matrix created from the model-specific optimal contrasts and define the matrix D as $D = C' S C$. This matrix is the covariance matrix for the optimal contrasts. The test statistic for assessing the significance of the optimal contrast based on the i th model is given by

$$t_i = \frac{c'_i \hat{\mu}}{c'_i S c_i}, i = 1 \dots, 7.$$

These test statistics follow a multivariate t distribution with an infinite degrees of freedom and correlation matrix $A^{-1} D A^{-1}$, where $A = \sqrt{\text{diag } D}$, i.e., A is a diagonal matrix constructed by finding the diagonal elements of D and computing the square root.

The set of significant dose-response models is selected by comparing each test statistic to an adjusted critical value q . This critical value is found from the joint distribution of the test statistic under the global null distribution of no dose-response effect for any of the seven pre-defined models. In other words,

$$P(\max(t_1, \dots, t_7) \geq q) = \alpha,$$

where α is a one-sided Type I error rate ($\alpha = 0.025$).

If the set of significant dose-response models is non-empty, the best dose-response model is chosen as the model corresponding to the most significant test statistic. Let k denote the index of the best dose-response model.

Once the best dose-response model is identified, it is fitted to the covariate-adjusted mean effects using the method of weighted least squares (WLS), i.e., the model is fitted by minimizing the following WLS criterion

$$(\hat{\mu} - f_k(d, \beta))' S^{-1} (\hat{\mu} - f_k(d, \beta))$$

with respect to the vector of model parameters β .

If relevant, modelisation will be done even if no dose-response model is significant.

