3.4.1. Statistical hypotheses

The statistical hypothesis is based on a multi-contrast test.

The hypothesis of the test is:

$$H_0: c'\mu = 0 \text{ vs } H_1: c'\mu > 0.$$

Where:

- μ is a vector of mean response.
- c is a vector of contrast.

Due to the use of the MCPMod methodology, the overall Type I error rate across the assumed dose-response relationships will be controlled at a one-sided 2.5% level.

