- $S^2 = \sum_{i=1}^k \sum_{j=1}^{n_i} \frac{(Y_{ij} - \bar{Y}_i)^2}{N - k}$
- c_m is the vector of contrasts with $\sum_{i=1}^k c_{mi} = 0$

The dose-response tests identify the set of clinically relevant models. A multiplicity adjustment is taken into account in the MCP-step. The joint distribution of the m test statistics is taken into account to compute an adjusted critical value that defines the threshold for statistical significance.

Under the global null hypothesis of no treatment effect under any model, the test statistics follow a central multivariate t distribution with $N - k$ degrees of freedom and correlation matrix R . More details for matrix R are given in Appendix 5.3.1.

To derive the multiplicity-adjusted critical value, denoted by q , let $T_1; \dots; T_m$ denote the random variables that have the same joint distribution as $t_1; \dots; t_m$ under the global null hypothesis. The adjusted critical value q is found from :

$$\Pr(T_{max} > q) = \alpha$$

Where α is the pre-specified Family Wise Error Rate (FWER) level equal to 0.025 (one-sided test).

The set of clinically relevant dose-response model corresponds to the models associated with $t_i > q$. The adjusted p-value will be calculated according to the value of q .

Among the set of clinically relevant dose-response models, the best dose-response contrast will be identified as the contrast test with the maximum test statistics.

An estimation of parameters of the best model selected will be provided according to the observed data as well as a plot of this model.

If relevant, modelisation will be done even if no dose-response model is significant.

Multiplicity issues:

The multiplicity issue due to multiple dose-response models is corrected with the computation of an adjusted critical value and adjusted p-values.

Missing data handling: missing data will not be imputed.

Statistical elements:

Finally, the following elements will be provided in summary tables:

- Descriptive statistics and 95% CI of the primary criterion in each arm.
- The best dose-response selected.
- An estimation of parameters of the best model selected.

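### The covariate-adjusted MCPMod sensitivity analysis uses infinite degrees of freedom (error about 2.7% to 2.8%, not 2.5%) and prints a variance where a standard error belongs; the primary test is unaffected

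*SAP*

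**What the plan says.** SAP 3.4.2.2 lists the MCPMod method adjusted for diabetes status and the combined prognosis criteria as a sensitivity analysis in the FAS. SAP 5.3.2 gives the details. The endpoint is taken as normal, an ANCOVA without intercept is fitted, and S is said to "denote the covariance matrix for these mean effects estimated from the ANCOVA model". The covariance matrix of the seven optimal contrasts is D = C'SC.

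Two statements follow:

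- The statistic for model i is printed as t_i = c_i'μ̂ / (c_i'Sc_i), with no square root.
- The reference distribution is given as: "These test statistics follow a multivariate t distribution with an infinite degrees of freedom and correlation matrix" A⁻¹DA⁻¹. Here A "is a diagonal matrix constructed by finding the diagonal elements of" D and taking their square roots. The critical value q is set at a one-sided α of 0.025.

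For the primary analysis, SAP 5.3.1 says that under the global null "the test statistics follow a central multivariate t distribution with $N - k$ degrees of freedom". Its statistic divides the contrast by S√(Σc²/n), a standard error (here S is the pooled standard deviation). SAP 3.4.1 states that "the overall Type I error rate across the assumed dose-response relationships will be controlled at a one-sided 2.5% level".

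**The concern.** Infinite degrees of freedom amount to treating the residual variance as known. Here it is estimated from at most 121 patients, and the SAP allows for that in the primary analysis but not in the adjusted one. The critical value is therefore slightly too small and the adjusted p-values slightly too favourable.

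The printed denominator is a different problem. Since D is the covariance matrix of the contrasts, c_i'Sc_i is a variance. A contrast divided by its variance is not a t statistic and changes with the unit of the data. It also conflicts with the correlation matrix A⁻¹DA⁻¹, which is right only for contrasts divided by their standard errors.

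At stake is the calibration of the only covariate-adjusted test of the primary endpoint. Its purpose is to be read beside the primary result.

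**Working it through.** **Inputs.** One-sided α 0.025, seven candidate models, six doses, SD 42 points and response from 32.5% to 62.5% (SAP 1.3, 5.3.1, 5.3.2). Two covariates with two levels each (SAP 1.2.2, 5.3.2). 121 patients included and a planned exclusion rate of 20% (SAP 1.3). Endpoint in percent, 100 × change / baseline (SAP 3.1.2).

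**Assumptions.** The FAS size is not given. I use N = 121 (everyone included), N = 97 (0.8 × 121 = 96.8) and N = 80 (a lower case), with equal groups.

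**Step 1: reproduce the plan's own figure.** With 27 per group the unadjusted test has 6 × 27 − 6 = 156 degrees of freedom. Simulation gives q = 2.399, minimum power 81.4% (Emax2) and 90.7% under the logistic model. The SAP states at least 80% and about 90%, so the contrasts used here match the plan.

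**Step 2: residual degrees of freedom.** Six dose means plus two binary covariates are eight parameters, which leaves N − 8.

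**Step 3: effect of infinite degrees of freedom, with the standard-error statistic.** q solves P(max T > q) = 0.025 over the seven correlated contrasts (4 million draws). With infinite degrees of freedom q = 2.376.

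| N | df = N − 8 | q with N − 8 | error if q = 2.376 is used |
|---|---|---|---|
| 121 | 113 | 2.407 | 2.70% |
| 97 | 89 | 2.416 | 2.75% |
| 80 | 72 | 2.425 | 2.82% |

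Repeat runs differ only in the third decimal of q. Even at N = 60 the error would be 2.94%.

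**Step 4: check by simulating the whole ANCOVA under the null.** 200,000 trials per run, with covariate prevalences of about 30% and 25% (assumed). With infinite degrees of freedom the error is 2.66% and 2.73% at N = 121, and 2.71% and 2.74% at N = 97. With N − 8 it is 2.47% to 2.54%. Simulation error is about √(0.027 × 0.973 / 200,000) = 0.04 points per run.

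**Step 5: the printed denominator taken literally.** The contrasts have unit length, so with equal groups of n the standard error of each is about SD/√n, and the printed statistic is the conventional t divided by that standard error. With n = 20 (121/6 ≈ 20):

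- Percent scale: SE = 42/√20 = 9.39. A conventional t of 2.376 × 9.39 = 22.3 is needed to pass q. Simulated error and power are both about 0% under every candidate model, against power of 68% to 83% for the standard-error statistic with N − 8.
- Fraction scale: SE = 0.42/√20 = 0.094. A conventional t of only 2.376 × 0.094 = 0.22 is needed, and the simulated error is about 65%.

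The literal formula is therefore not calibrated to any α.

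**The case against.** The strongest reply has four parts.

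*The primary error rate is untouched.* This stands. A reader might infer from SAP 3.4.1 that the promise that error "will be controlled at a one-sided 2.5% level" fails for the trial. The documents do not support that. The promise sits with the hypotheses of the primary MCPMod test, for which SAP 3.4.2.1 says "the test statistics follow a central multivariate t distribution with" N − k degrees of freedom and prints a standard-error denominator. Section 5.3.2 is a sensitivity analysis.

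*The two departures do not add up.* This also stands. A reader might infer that together they inflate the error. Infinite degrees of freedom alone are slightly liberal. The variance denominator on the percent scale makes the test almost never reject. They pull in opposite directions and cannot both describe the behaviour of one implementation.

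*The missing root is a slip that the section itself resolves.* Largely accepted. A = √diag(D) and the primary statistic both imply standard errors, and SAP 5.4 assigns the computation to the DoseFinding package. Loss of the root when the PDF was read cannot be excluded either. But SAP 5.4 states neither the form of the statistic nor the degrees of freedom, so the formula in 5.3.2 is the only written specification.

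*A normal reference is openly pre-specified and defensible for a supportive analysis of this size.* Partly accepted. The excess is small, and a reader who concludes that the two analyses cannot be compared goes too far. The technical difference matters only if the maximum statistic falls in a window 0.03 to 0.05 wide (2.376 to between 2.407 and 2.425), and the analyses already differ by design in means and contrasts. Still, the SAP states 0.025 without calling it approximate, and gives no reason for departing from its own primary rule.

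**Conclusion.** The point holds as a correction to a sensitivity analysis. With the standard-error statistic, infinite degrees of freedom give a family-wise error of about 2.7% (N = 121) to 2.8% (N = 97 or 80) instead of 2.5%, an excess of 0.2 to 0.3 points. This rests on near-equal groups and on assumed FAS sizes. The printed variance denominator is probably a notation error. What the software call will compute cannot be told from the documents, so its literal consequences are conditional. Nothing here weakens the primary test.

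**What to change.** In SAP 5.3.2, print the statistic as t_i = c_i'μ̂ / √(c_i'Sc_i). Take q and the adjusted p-values from the multivariate t with the ANCOVA residual degrees of freedom, N minus six dose means minus two covariates, and state that this value is passed explicitly to the software. If the normal reference is kept, say that it is an approximation with a true level of about 2.7% to 2.8%.

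The cost is two lines of text and one software argument. The critical value rises from 2.38 to about 2.41 to 2.43. At 20 per group, power falls by about 1 point (for example from 69.4% to 68.2% under Emax1).

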5.4. Software and programming codes

MCPMod analyses and the MED determination will be performed with the “DoseFinding” package using the [R® software](#). Seed parameter will be set at 1234.

Others statistical analyses will be performed using SAS®/PC Software version 9.2.

